3.2.2.2. Laboratory Data

Detailed descriptions of the laboratory data and other tests that are collected per protocol can be found in Table 5 ("Clinical Laboratory Tests") of Protocol C5041011 (APD334-210) amendment 2.0.

3.2.3. PK Endpoints

Plasma concentrations of etrasimod will be assessed from samples collected pre-dose and 4 hours post-dose (after 12-lead ECG) on Week 0/Day 1, and pre-dose (trough) at Weeks 2, 4, 8, 12, 16, 24, 32, 48, 52, and ET (only required if ET visit ≤ 30 hours since last treatment administration), and at the 2-Week and 4-Week Follow-Up visits (for participants not enrolled into any extension study). A PK sample should also be drawn, if possible, at the time of any SAE or adverse event leading to study treatment discontinuation.

Plasma samples may also be used for profiling of drug binding proteins, bioanalytical method validation purposes, stability assessments, or to assess other actions of etrasimod with plasma constituents.

3.3. Other Safety Endpoint(s)

3.3.1. 12-lead ECGs

ECGs are recorded on a 12-lead ECG machine and read locally and centrally. The following ECG parameters are reported for this study:

• HR (bpm)

- PR interval (ms)
- RR interval (ms)
- QRS interval (ms)
- QT interval (ms)
- QTcF interval (ms)
- AV conduction abnormalities
 - First-degree AV Block
 - First-degree AV Block with PR>230ms
 - Second-degree AV Block Type 1
 - Second-degree AV Block Type 2
 - Third-degree AV Block or Higher

3.3.2. Cardiac Holter Endpoints

3.3.2.1. Binary Endpoints

- Incidence of mean hourly heart rate based on Holter recording (hHR) recovery.
 - Note: hHR was generated by the cardiac central laboratory for each 60-minute interval based on date/time of first dose and Holter recording date/time, with hour 1 starting at the time of dosing. See Section 9.1.7 for additional detail on how partial hourly interval is handled by the cardiac central laboratory and how hourly timepoint will be programmatically derived. For the analysis purpose, if hHR was associated with a time interval of <10 minutes, then its value will be set to missing for the summary. Per cardiac central laboratory, if the Holter recording was started < 60 seconds prior to dosing, then no pre-dose record is derived for the participant. In such case, all the Holter recording will contribute to post-dose calculation only.

- Incidence of low heart rate over the entire Holter monitoring period and at each post-dose hourly timepoint defined by:
 - hHR <40
 - hHR <50
 - hHR <50 bpm plus > 10 bpm decrease from baseline
- Incidence of first nadir hHR reached at each post-dose hourly timepoint

- Incidence of additional abnormal findings flagged by cardiac central laboratory
 - Mobitz I 2nd Degree AV Block
 - Mobitz II 2nd Degree AV Block
 - 2:1 AV Block
 - High Grade AV Block
 - Complete Heart Block
 - Varying Conduction Ratio AV Block
 - Evidence of new onset of transient bundle branch block (BBB) or Intraventricular conduction delay
 - Other specified (any abnormality detected other than the list above must be specified under "Other" and alert notified at discretion of reading Cardiologist)

3.3.2.2. Continuous Endpoints

- hHR and change from baseline by post-dose hourly timepoint
- Time to first nadir hHR (based on Holter hourly data)

3.3.3. Vital signs

The following vital signs measurements are reported for this study:

- Systolic blood pressure (SBP) (mm Hg)
- Diastolic blood pressure (DBP) (mm Hg)
- Heart rate (bpm)
- Respiratory rate (resp/min)
- Temperature (°C), where Temperature (°C) = (5/9) (Temperature (°F) 32)

3.3.4. Pulmonary Function Tests

The following pulmonary function tests (PFT) measurements (actual and % predicted) will be reported for this study:

- FEV1
- FVC
- Total Lung Capacity (TLC)

- FEV1/FVC ratio
- Forced Expiratory Flow (FEF) 25-75
- DLCO (if available)

3.3.5. Ophthalmoscopy and Optical Coherence Tomography (OCT)

Ophthalmoscopy and OCT assessment will be performed according to the Schedule of Assessments (Table 6 in Protocol C5041011 (APD334-210) amendment 2.0 Appendix 1). The endpoint is the categorical result in ophthalmoscopy with OCT parameters by visit (the categories are listed on the eCRF).

3.4. Other Endpoints

3.4.1. Exploratory Efficacy Endpoints

- Symptomatic remission at each study visit (Weeks 2, 4, 8, 12, 16, 24, 32, 40, 48, and 52). Two symptomatic remission derivations described in Section 3.2.1 will be applied, respectively.
- Symptomatic response at each study visit (Weeks 2, 4, 8, 12, 16, 24, 32, 40, 48, and 52). Symptomatic response is defined as ≥ 30% decrease from baseline in composite RB and SF subscores. Its derivation will be based on the following 2 approaches, respectively.
 - Symptomatic response 1, based on RB and SF derivation per protocol (Derivation 1, Section 3.1.1)
 - Symptomatic response 2, based on RB and SF derivation per FDA
 Draft Guidance (Derivation 2, Section 3.1.1)
- Clinical remission at Week 52 among participants achieving clinical response at Week 12. Three derivations for clinical remissions described in Section 3.1.3 will be applied, respectively.
- Reduction from baseline in both ES and RB or in both ES and SF at Week 52.
 Derivation 1 and 2 for RB and FS in Section 3.1.1 will be applied, respectively.
- Clinical response based on total Mayo score (TMS) at Week 52. The TMS includes all four components (ES, RB, SF and PGA) of the MCS. The total score range of the TMS is from 0 to 12 with each component ranging from 0 to 3 (0 = normal, 1 = mild, 2 = moderate, 3 = severe) and higher scores indicating more severe disease. Clinical response based on TMS is defined as a ≥ 3-point and ≥ 30% decrease from baseline in TMS, and a ≥ 1-point decrease from baseline in RB subscore or an absolute RB subscore ≤ 1. The TMS will be derived based on each of derivations for RB and SF (as defined in Section 3.1.1), respectively.
 - TMS clinical response 1, based on RB and SF derivation per protocol (Derivation 1, Section 3.1.1)
 - TMS clinical response 2, based on RB and SF derivation per FDA Draft Guidance (Derivation 2, Section 3.1.1)

- Histologic response based on Geboes Grading System at Week 52.
- Histologic remission based on the Geboes Grading System at Week 12. Histologic remission based on the Geboes Grading System is define as Geboes Score (GS) \leq 2.0
- Histologic remission based on the Geboes Grading System at Week 52
- Histologic response based on the RHI at Week 52.
- Histologic remission based on the RHI at Week 12. Histologic remission based on RHI is defined as a RHI score ≤ 3 with lamina propria neutrophils subscore = 0 and neutrophils in epithelium subscore = 0
- Histologic remission based on the RHI at Week 52
- Clinical remission based on the Ulcerative Colitis 100 (UC-100) index at Week 12. UC-100 index is based on SF subscore, ES, and RHI score. These 3 components are incorporated into a calculable final index. The formula for the composite UC-100 score is: (1 + 16 × SF subscore [0 to 3] + 6 × ES [0 to 3] + 1 × RHI score [0 to 33]).

Clinical remission based on the UC-100 index is defined as UC-100 index \leq 25. Its derivation will be based on the following 2 approaches, respectively.

- UC-100 clinical remission 1, based on RB and SF derivation per protocol (Derivation 1, Section 3.1.1)
- UC-100 clinical remission 2, based on RB and SF derivation per FDA Draft Guidance (Derivation 2, Section 3.1.1)
- Clinical remission based on the UC-100 index at Week 52. Two UC-100 clinical remissions described above will be applied, respectively.
- Clinical remission based on the TMS at Week 12. Clinical remission based on TMS is defined as a TMS ≤ 2 with all subscores ≤ 1 . Its derivation will be based on the following 2 approaches, respectively.
 - TMS clinical remission 1, based on RB and SF derivation per protocol (Derivation 1, Section 3.1.1)
 - TMS clinical remission 2, based on RB and SF derivation per FDA Draft Guidance (Derivation 2, Section 3.1.1)
- Clinical remission based on the TMS at Week 52. Two TMS clinical remissions described above will be applied, respectively.
- MMS and Change from Baseline by visit. Derivations 1 and 2 for MMS in Section 3.1.1 will be applied, respectively.
- RB, SF, and composite RB/SF subscores and change from Baseline by visit. Derivations 1 and 2 for RB and SF in Section 3.1.1 will be applied.

- Clinically meaningful improvement in bowel urgency at Week 12 and Week 52: Decrease from baseline in Urgency NRS ≥ 3 points.
- Bowel urgency remission at Week 12 and Week 52: Urgency NRS \leq 1 point.
- Complete bowel urgency remission at Week 12 and Week 52: Urgency NRS = 0 point.

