10.8.1. Exploratory Efficacy Endpoints

Exploratory efficacy endpoints are:

- The proportion of subjects achieving symptomatic remission at each study visit (Weeks 2, 4, 8, 12, 16, 20, 24, 32, 40, 48, and 52)
- The proportion of subjects achieving symptomatic response at each study visit (Weeks 2, 4, 8, 12, 16, 20, 24, 32, 40, 48, and 52)
- The proportion of subjects achieving clinical remission at Week 52 among subjects achieving clinical response at Week 12
- The proportion of subjects with reduction from baseline in both ES and RB OR in both ES and SF at Week 52
- The proportion of subjects achieving complete symptomatic remission at Week 12 (RB subscore = 0 and SF = 0)
- The proportion of subjects achieving complete symptomatic remission at Week 52 (RB subscore = 0 and SF = 0)
- The proportion of subjects achieving endoscopic improvement at Week 52
- The proportion of subjects achieving a clinical response based on TMS at Week 52

- The proportion of subjects achieving histologic response based on Geboes Grading System at Week 52
- The proportion of subjects achieving histologic remission based on the Geboes Grading System at Week 12
- The proportion of subjects achieving histologic remission based on the Geboes Grading System at Week 52
- The proportion of subjects achieving histologic response based on the RHI at Week 52
- The proportion of subjects achieving histologic remission based on the RHI at Week 12
- The proportion of subjects achieving histologic remission based on the RHI at Week 52
- The proportion of subjects achieving clinical remission based on the UC-100 index at Week 12
- The proportion of subjects achieving clinical remission based on the UC-100 index at Week 52
- The proportion of subjects achieving clinical remission at both Weeks 12 and 52
- Clinical remission based on the TMS at Week 12
- Clinical remission based on the TMS at Week 52

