2.2.3. Primary Estimand (Estimand 1)

The primary estimand of this study is a composite estimand, which estimates the effect of randomized treatment accounting for treatment adherence and response.

- Treatment: Etrasimod 2 mg vs Placebo
- Population: Participants with mildly to moderately active UC as defined in 2022
 FDA Draft Guidance; Ulcerative Colitis: Developing Drugs for Treatment (Section 8 References)
- Variable: primary efficacy endpoint of clinical remission at week 52 and all binary efficacy endpoints as described in Sections 3.1, 3.2.1 and 3.4.1
- Intercurrent events: the following intercurrent events are defined:
 - 1) Discontinue the study treatment during the double blind treatment period for any reasons
 - 2) Initiate a rescue medication for UC (Section 9.3)
 - 3) Have an increase in dose over baseline levels in their existing UC medication following the rules in Section 9.3

4) Have a rescue non-drug treatment (eg, colectomy, ileostomy, or sigmoidectomy) during the study (Section 9.3)

Participants having any of the intercurrent events as defined in 1) - 4) above will be considered as nonresponders, that is, have a known outcome of nonresponse at applicable timepoints. Missing measurements due to other reasons will be treated as missing. The method of dealing with missing data is presented in Section 5.3

 Population-level summary: Proportion of participants who are responders in each treatment group and differences in proportions of responders between Etrasimod 2 mg group and placebo group.

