5. GENERAL METHODOLOGY AND CONVENTIONS

5.1. Hypotheses and Decision Rules

There are multiple null hypotheses for the comparison of etrasimod 2 mg versus placebo for the following primary endpoint and key secondary efficacy endpoints. The family-wise typeI error rate will be controlled at the level of 0.05 using the fixed sequential testing approach in the order specified below.

- (1) Clinical remission at Week 52 (Primary efficacy endpoint)
- (2) Endoscopic improvement at Week 52
- (3) 12-week corticosteroid-free clinical remission at Week 52
- (4) Clinical remission at Week 12
- (5) Endoscopic improvement at Week 12
- (6) Sustained clinical remission (clinical remission at both Week 12 and Week 52)
- (7) Histologic-Endoscopic Mucosal Improvement at Week 52
- (8) Complete symptomatic remission at Week 52
- (9) Complete symptomatic remission at Week 12

Hypotheses for all other efficacy endpoints not described above are to be tested at the nominal 5% (2-sided) significance level, without adjusting for multiple comparisons.

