5.2.1. Analyses for Binary Efficacy Endpoints

The primary analysis of all binary efficacy endpoints will be performed based on the Mantel–Haenszel (MH) weighted method, stratified by (a) naïve to biologic or JAK inhibitor therapy at study entry (yes or no) and (b) baseline corticosteroid use (yes or no). Results will be presented as the number of participants with response, proportion of participants with response, estimated common risk difference and associated two-sided 95% confidence intervals (CIs), and p-values from the MH weighted method.

For (a) and (b) mentioned above that are used in MH weighted method, the reported strata (which are based on randomization system) will be used for the statistical analyses. Analyses may be repeated using actual strata (which are based on medications reported in eCRF) if the strata data recorded in the randomization system and the actual strata data recorded in the

CRF are inconsistent for more than 10% of the randomized participants. i.e., if there are more than 10% of randomized participants whose reported strata are not the same as actual strata.

The methods for handling with missing data are described in Section 5.3 below.

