Other secondary efficacy endpoints (Section 3.2.1)	Same as primary endpoint	Same as primary endpoint	N/A	N/A
Exploratory efficacy endpoints: binary endpoints (Section 3.4.1)	Same as primary endpoint	Same as primary endpoint	N/A	N/A
Exploratory efficacy endpoints: continuous endpoints (Section 3.4.1)	linear mixed-effect model based on PAS (Section 5.2.2)	Data will not be imputed explicitly, assuming MAR (Section 5.3.2)	N/A	N/A
HRQoL endpoints (Section 3.4.2)	Same as continuous exploratory efficacy endpoint	Same as continuous exploratory efficacy endpoint	N/A	N/A
Efficacy-related biomarker endpoints (Section 3.4.3)	Same as continuous exploratory efficacy endpoint except that the analysis for lymphocyte counts will be based on Safety Set, not PAS	Same as continuous exploratory efficacy endpoint	N/A	N/A

For continuous endpoint, line plots over time for LS mean and SE by treatment will be provided if deemed appropriate.

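### The exploratory comparison of Week 52 remission among Week 12 responders is planned with a risk difference, interval and p-value, but it is not a randomized comparison

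*SAP*

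**What the plan says.** The endpoint is exploratory in both documents. Protocol 10.8.1 words it as "The proportion of subjects achieving clinical remission at Week 52 among subjects achieving clinical response at Week 12"; SAP 3.4.1 keeps it as "Clinical remission at Week 52 among participants achieving clinical response at Week 12" and applies three remission derivations.

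The analysis is assembled from three places:

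- SAP Table 7 (Section 6.1) has one row for "Exploratory efficacy endpoints: binary endpoints (Section 3.4.1"). It sets both the main analysis and the missing-data handling equal to those of the primary endpoint, and marks sensitivity and supplementary analyses as not applicable.
- SAP 5.2.1 states: "The primary analysis of all binary efficacy endpoints will be performed based on the Mantel–Haenszel (MH) weighted method". The output includes the "estimated common risk difference and associated two-sided 95% confidence intervals (CIs), and p-values from the MH weighted method".
- SAP 5.1, after the nine-step fixed sequence, states: "Hypotheses for all other efficacy endpoints not described above are to be tested at the nominal 5% (2-sided) significance level, without adjusting for multiple comparisons".

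SAP 2.2.3 lists every binary endpoint of Section 3.4.1 as a variable of Estimand 1, which "estimates the effect of randomized treatment accounting for treatment adherence and response". The population of that estimand is participants with mildly to moderately active UC, with no restriction to Week 12 responders.

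Clinical response at Week 12 is defined in SAP 3.2.1 from the fall in modified Mayo score since baseline plus a rectal-bleeding condition. It is itself one of the other secondary efficacy endpoints. Nothing in either document marks the responder-only endpoint as descriptive, acknowledges the conditioning, or defines an estimand for responders.

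**The concern.** Randomization makes the arms comparable at baseline. It does not make the Week 12 responders of one arm comparable with those of the other when treatment influences who responds. Placebo responders are people who improve without the drug. If etrasimod raises response, its responders include others who would not have improved on placebo, and these may have a better or worse outlook for Week 52. Stratifying by prior biologic or JAK inhibitor exposure and by baseline corticosteroid use corrects only for those two factors.

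The documents give reason to expect such an influence. Protocol 3.2 reports a Phase 2 difference from placebo in Week 12 modified Mayo score of -0.99 (SE 0.42, p = 0.0091). Protocol 1.2 reports Phase 3 improvements on clinical, endoscopic and symptomatic endpoints.

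At stake is how one exploratory table is read. Its risk difference and p-value would look like a treatment effect on durability, and could show a loss where the drug helps or a gain where it adds nothing at Week 52.

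**Working it through.** **Inputs from the documents.** The plan states no figure for this endpoint and no Week 12 response rates. From the sample-size paragraph (Protocol 10.2) I take 122 and 61 participants and Week 52 remission of 34% and 14%. That paragraph's claim of at least 80% power by Fisher's exact test reproduces: exact enumeration gives 83.8%. All response rates below are assumptions.

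**Step 1: the sign can reverse.** Assume 30% of participants would respond at Week 12 in either arm and remit at Week 52 with probability 0.60. Assume a further 25% respond only on etrasimod and remit with probability 0.35, and nobody responds only on placebo.

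- Among responders, placebo: 0.60.
- Among responders, etrasimod: (0.30 × 0.60 + 0.25 × 0.35) / (0.30 + 0.25) = 0.2675 / 0.55 = 0.486.
- Responder-only difference: 48.6% − 60% = −11.4 points.
- Response at Week 12 and remission at Week 52 over everyone: 0.2675 against 0.30 × 0.60 = 0.18, a gain of 8.75 points.

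This example gives the drug no benefit in those who respond in either arm. For the responder-only rates to be equal, their remission probability on etrasimod would have to be (0.60 × 0.55 − 0.0875) / 0.30 = 0.81. Under these inputs, a benefit to them of up to about 21 points would still not show as a gain.

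**Step 2: the bias can go either way.** Take two equal prognostic classes (good / poor) and give each class the same Week 52 remission probability in both arms, so the true effect on remission is zero. The rate among responders in an arm is the class-weighted sum of response × remission, divided by the class-weighted sum of response. Row A, etrasimod: (0.5 × 0.80 × 0.40 + 0.5 × 0.40 × 0.08) / 0.60 = 0.176 / 0.60 = 29.3%. Rejection is the share of 40,000 simulated trials of 122 and 61 with two-sided p below 0.05, by an unstratified pooled z-test.

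| | Response on etrasimod (good/poor) | Response on placebo (good/poor) | Remission (good/poor) | Responder-only rates, etrasimod vs placebo | Difference (points) | Rejection |
|---|---|---|---|---|---|---|
| A | 80% / 40% | 60% / 10% | 40% / 8% | 29.3% vs 35.4% | −6.1 | 9.3% |
| B | 70% / 50% | 60% / 10% | 60% / 8% | 38.3% vs 52.6% | −14.2 | 22.2% |
| C | 85% / 35% | 35% / 35% | 40% / 8% | 30.7% vs 24.0% | +6.7 | 7.9% |
| D | 90% / 30% | 35% / 35% | 60% / 8% | 47.0% vs 34.0% | +13.0 | 18.1% |
| E | 60% / 10% | 60% / 10% | 60% / 8% | 52.6% vs 52.6% | 0 | 5.0% |

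Differences are taken before rounding. In the same scenarios the test over all 183 participants rejects in 4.8% to 5.0% of trials. Row E isolates the cause: when the drug leaves Week 12 response unchanged in each class, the bias disappears.

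**Step 3: the planned effect seen through this endpoint.** Suppose, again as an assumption, that every Week 52 remitter was a Week 12 responder. With response of 70% and 30%, the planned 34% against 14% becomes 0.34/0.70 = 48.6% against 0.14/0.30 = 46.7%, or 1.9 points, in about 85 and 18 people. With response of 50% in both arms it becomes 68% against 28%, or 40 points. The same 20-point effect yields very different figures, depending on Week 12 response.

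**The case against.** The strongest reply is that the endpoint is exploratory, sits outside the fixed sequence and supports no confirmatory claim. That is correct, and it limits the weight of the point. It does not answer it: the exploratory label deals with multiplicity, whereas the difficulty here is that the difference and interval do not estimate an effect of randomized treatment.

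A second reply is that the drug's effect on Week 12 response is not established here. That also stands. The Phase 2 and Phase 3 results concern moderately to severely active UC, the Phase 2 figure is a mean score difference rather than a response rate, and the documents give no response rates for a population with modified Mayo score 4 to 6. An effect is expected, not shown.

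Third, a joint endpoint over everyone answers a different question from durability among responders, and Week 52 remission and sustained remission already give comparisons over the whole set. This is fair, so descriptive reporting is the main remedy and the joint test is optional.

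A reader might infer three stronger things that the documents do not support:

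- That the primary conclusion or the type I error control is compromised. Neither uses this endpoint.
- That the comparison must work against etrasimod. Rows C and D show the opposite.
- That every endpoint restricted to a subset shares the fault. The subsets defined by baseline corticosteroid use are fixed before randomization and do not.

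**Conclusion.** The point holds, with limited reach. The SAP assigns a between-arm risk difference, interval and p-value to a subset chosen by a post-randomization efficacy outcome, and places it under an estimand whose population is not that subset. The comparison is not protected by randomization. Under the assumed inputs with zero true effect on Week 52 remission, the spurious difference ran from −14.2 to +13.0 points and the nominal 5% test rejected in 7.9% to 22.2% of trials. These sizes are illustrations; the actual bias depends on Week 12 response rates and prognosis that the documents do not give, and is zero if the drug changes nobody's Week 12 response. What the endpoint shares with the primary is the method and the nonresponder rule, not the place in the testing order or the sensitivity analyses. The change should be made, but the trial's main conclusions do not depend on it.

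**What to change.** In SAP 3.4.1 and Table 7, take this endpoint out of the general row for exploratory binary endpoints. Report the number and proportion in Week 52 remission among Week 12 responders by arm as descriptive only. Per-arm intervals are acceptable; a between-arm risk difference, its interval and a p-value are not. Add a sentence saying that this is not a randomized comparison, and exclude the endpoint from the variables of Estimand 1 in Section 2.2.3. While editing, name which of the two clinical response derivations in Section 3.2.1 defines the subset, since Section 3.4.1 specifies only the remission derivations.

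If a test is wanted, define the variable as clinical response at Week 12 and clinical remission at Week 52, with the whole Primary Analysis Set as denominator. Sustained clinical remission already has this form.

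Record the departure from Protocol 10.8.1 in SAP Table 2. The cost is the loss of the conditional p-value, revised outputs for the three remission derivations, and a few lines of SAP text. No new data are needed.
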